**Potential risks include the following:**

The potential patient risks are discussed below:

1. Phlebotomy. All studies involve the withdrawal of blood. In no instance will this exceed 600 ml within a two month period. Any subject who has donated blood over the two month period prior to study will be excluded from participating. If a subject participates in a study, he/she will be told he/she should not donate any blood for the study duration. Any subject with a hematocrit less than 33% will be excluded from study. Infection is possible with venipuncture but rare (<1%). Venipuncture will be performed by inserting a single, small needle into a vein in the subject's arm after cleaning the local area with isopropyl alcohol. This procedure will be performed by trained staff members with extensive experience in venipuncture. Mild pain during the blood draw is common but temporary. Local hematomas occur in about 1% of subjects.

2. Administration of Insulin and Glucose. Since the glucose infusion is designed to counterbalance the metabolic effects of insulin, hypoglycemia will not occur. No other side effects of insulin and glucose are known. Plasma glucose concentration will be determined at 5 min intervals throughout the period of insulin/glucose administration. There is a possibility that the insulin clamp will not be performed if unable to establish IV access (most common reason) or for any other reason precluding its completion at the discretion of the PI.

3. IV lines. Catheters will be placed in an antecubital vein and a hand vein for the euglycemic clamps. If the euglycemic clamp is not performed, an IV may be placed if a biopsy is performed. Local hematomas occur in about 1% of catheterization. Infection is possible (<1%), but we have not experienced this complication. One instance of thrombophlebitis has been observed (<1%). The hand with the catheter will be placed in a warm (55° C) transparent plastic box to arterialize venous blood. We have observed one instance of skin burning (2nd degree) using these boxes (<0.01%).

4. Muscle biopsy. At the time of biopsy, subjects may feel pain, discomfort, or pressure (variably described by different subjects) for about 5-10 seconds. Pain or discomfort ceases as soon as the cannula is withdrawn. These will be performed by trained, experienced staff, either an MD or Nurse Practitioner. Over the last 20 years, our group has experience with approximately 1300 biopsies. Local hematomas occur in <2% of subjects. One patient experienced a moderately painful hematoma that resolved within 2 weeks (0.1%). About 1 in 50 subjects report non-clinically evident numbness or altered sensation at the biopsy site, which is transient. All subjects will return to the clinical research unit within 7 days to evaluate the biopsy site. On any particular day, the muscle biopsy is performed twice, once in a fasting state, and then lastly after exposure to insulin during the insulin clamp, in order to measure muscle

tissue insulin signaling response. There is the possibility that a future biopsy may not be done at the discretion of the PI in case the subject did not tolerate well a prior biopsy.

5. Frailty assessment, SPPB, and 6-MWT. There is minimal risk to the physical measurements of frailty assessment, which includes measurement of strength (hand grip using handheld dynamometer; knee extension using a seated computerized dynamometer) and 10-foot walking speed at usual pace. The risk associated with grip strength measurement is that some subjects may have some slight muscle or joint soreness that should resolve by itself within hours or a few days. It is possible that some subjects may experience transient fatigue and/or pain in the legs associated with walking 10 feet, which should resolve within minutes to hours. To minimize risk of falls during the 10-foot walk, the study investigator or trained study personnel will walk side-by-side with the subject throughout the walk. Additionally, the study investigators or study personnel have experience working with older persons, and will be able to evaluate the subject's ability to walk independently and safely. If the subject does not appear capable of performing the 10 foot walk due to any reason (dizziness, lower extremity weakness) the procedure will not be performed. If the subject expresses concern and/or anxiety about performing the task, it will not be performed. If participants use an assistive device for ambulation, this may be used during the walking speed assessment. [name] has performed this assessment on approximately 80 subjects from the Air Force Villages retirement community with no adverse event or fall. The procedure is safe. The SPPB is a standardized assessment of lower extremity function, which includes standing balance, 4-meter walk (approximately 13 feet), and repeated standing from a seated position (chair stand). The battery has an excellent safety record. It has been administered to over 20,000 persons in various studies and no serious injuries are known to have occurred. The 6-MWT test is a well-established assessment that will be conducted in an unobstructed hallway utilizing a standardized script. Total distance covered and number and duration of rests and symptoms will be recorded. With this test, there is a risk of the participant losing their balance and falling. We will minimize this risk by: (1) safely escorting participants to chairs located along the walking course should they become unsteady; (2) following the participant at a close distance; and, (3) being nearby should the participant need assistance. Further, if a participant appears to have major difficulty or is unable to complete the shorter walking tests above, the 6-MWT will not be performed. The lower extremity strength testing is low risk to the participant as we are asking participants to extend their leg against resistance. There is possibility of mild discomfort during the test due to muscle exertion, but it is self-limiting and will resolve as soon as the test is stopped or the participant voluntarily reduces the amount of force applied.

6. Questionnaire data collection. Various standardized questionnaires will be used to obtain information relative to these analyses, including some information needed to ascertain frailty (physical activity level and self-reported exhaustion), a depression scale, and screen for cognitive impairment (Tariq et al., 2006). These are minimal risk to the participant but could result in mild psychological distress which should be transient and resolve. To minimize this risk, study personnel will be sure to inform participants that he/she can skip any question he/she prefers not to answer. All of the questions in the interview will be performed by a trained staff member or the PI, who is a geriatrician, to assure risks are minimal as would be the case in standard clinical care.

7. Administration of metformin. The administration of metformin in adults with normal renal function is safe, the inclusion/exclusion criteria have been tailored so as to reduce the possibility of adverse events. The most severe adverse event associated with metformin use is lactic acidosis which is very rare (occurs in < 1%), and is more common in patients with impaired renal function. Therefore, individuals with creatinine clearance <45 mL/min are excluded from this study based on FDA dosing recommendations. More common adverse reactions (occur in > 10%) are diarrhea, nausea, and vomiting. Subjects will be provided with the common side effects as part of informed consent and will be monitored closely throughout the study. The medication will be titrated to the maximum tolerable dose. Subjects who do not tolerate metformin will be disenrolled.

8. **Administration of pioglitazone.** Only subjects who convert to diabetes and whose hemoglobin A1C is over  $\geq 7.5$  despite metformin administration will receive pioglitazone. Subjects with hematuria on urinalysis or history of bladder malignancy will not be administered pioglitazone. Subjects with liver disease and elevated transaminases are excluded from the study. More common adverse reactions (occur in  $> 10\%$ ) are edema and upper respiratory tract infection. Patients will be evaluated with routine history and physical examinations to monitor for adverse reactions, and those with peripheral edema greater than 1+ or any evidence suggestive of heart failure will not receive pioglitazone.

9. **Radiation exposure.** Subjects will be exposed to a small amount of radiation during the insulin clamp and dual-energy x-ray absorptiometry (DEXA) exam (36.48 mrem), which is approximately 17% of the average amount of natural environmental radiation exposure (620 mrem dose) that each member of the general public receives per year. Tritiated glucose is given during the insulin clamp studies. The radiation exposure from tritiated glucose is well within guidelines (Shreve et al., 1958; U.S. Department of Commerce National Bureau of Standards Handbook 69, 1969). The cumulative radiation exposure is well within the dose range (1,000 mCi) approved by the University of Texas Health Science Center Radiation Safety Committee. At these low exposures, risk is minimal. If a participant has had exposure to radiation due to medical tests or treatments and the estimated total exposure within one year is expected to be  $> 1,000$  mCi, the insulin clamp and/or DEXA exam will not be performed at the discretion and estimation of the PI.

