i) Pharmacological intervention: After the baseline studies, subjects will be randomized to metformin (titrated up to 1000 mg twice daily, as tolerated) vs. placebo over a period of 6 months. Metformin and placebo are obtained from Major Pharmaceuticals (Livonia, MI). Randomization and drug preparation and dispensing will be performed by the Research Pharmacist of the BRU. Subjects will be initiated at 500 mg daily at Visit 2. Subjects will be seen in person at 1 week, and if tolerating metformin, will be directed to increase to 500 mg twice daily after 2 weeks. Phone calls will be made about every two weeks to titrate medications as tolerated as needed until patient is at maximum dose tolerated with goal dose of 1000 mg twice daily. At 3 months subjects will be seen in-person for a history & physical examination. OGTT will be performed every 6 months to monitor for diabetes conversion. Plasma metformin level will be measured once the participant has reached his/her maximum tolerated dose at either Visit 2, 4, 5, 6, 7, 8, 10, 11, 12, 13 or 14. If participants convert to diabetes and are started on metformin from placebo, an additional metformin level will be measured once the patient has reached his/her maximum tolerated dose at either Visit 2, 4, 5, 6, 7, 8, 10, 11, 12, 13, or 14. All patients will also receive patient education handouts about lifestyle modification to prevent diabetes at Visit 2.

j) Diet and exercise counseling: After the baseline visit, subjects will receive standard diet and exercise advice using resources available from the National Institute on Aging. This will be conducted by study staff member, [name], who is a certified diabetes educator. Resources will be given to subjects, including "Exercise & Physical Activity: Your Everyday Guide from the National Institute on Aging" available from <https://www.nia.nih.gov/health/publication/exercise-physical-activity/introduction>, and "What's On Your Plate? Smart Food Choices for Healthy Aging" available from <https://www.nia.nih.gov/health/publication/whats-your-plate>.

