k) Management of conversions: Any one of the following will prompt 2-hour OGTT to confirm possible diagnosis of diabetes: fasting glucose  $\geq$  126 mg/dL, HbA1c  $\geq$  6.5%, 2-hour OGTT glucose of  $\geq$  200 mg/dL, or clinical signs and symptoms of diabetes. If any of these occur, OGTT will be conducted within 6 weeks. If the subsequent 2-hour OGTT glucose is  $\geq$  200 mg/dL, diabetes conversion will be confirmed. If diabetes conversion occurs based on the OGTT, measurements of frailty, insulin sensitivity (clamp), body composition (DEXA), coagulation tests, stool sample, and inflammation (muscle and systemic) will be

performed. If these assessments are conducted within 1 month of the 12 month or 24 month assessments, the 12 or 24 month assessments will not be conducted. After these repeat measurements are performed, the study allocation will be unblinded, and, if receiving placebo, subjects will be initiated on metformin and titrated as above. Medication management will occur by an independent practitioner (MD or NP) on the study staff who is not the PI such that the PI will remain blinded to study treatment. Hemoglobin A1c will be monitored in those who have converted to diabetes, and, if it reaches  $\geq 7.5$ , subjects will be initiated on 15 mg pioglitazone in addition to metformin unless there is a contraindication to pioglitazone. The rationale for adding pioglitazone versus other antidiabetic agents is that the low dose metformin-thiazolidinedione combination has been shown to have a potent effect to prevent diabetes (Zinman et al., 2010). Pioglitazone will be increased to 30 mg if hemoglobin A1C remains  $\geq 7.5$ . Pioglitazone will not be initiated in any subject with the following: hematuria, history of bladder cancer, lower extremity edema  $> 1+$ , or known history of osteopenia or osteoporosis. Subjects will be seen every 3 months for monitoring of HbA1C. If maximal metformin (1000 mg BID) and pioglitazone (30 mg daily) doses are reached (or if the patient cannot tolerate metformin and/or pioglitazone) and HbA1C remains  $\geq 8$ , subjects will be referred to their primary care physicians for further treatment, but will remain in the study for frailty assessment and all other follow-up studies. Subjects who initially were on metformin will receive pioglitazone 15 mg (in addition to metformin) if Hemoglobin A1c reaches  $\geq 7.5$ , which will be titrated to 30 mg if necessary as described above.

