#### Data Analysis Plan:

### STATISTICAL METHODS & POWER CALCULATIONS

**Overview.** In all analyses for Aim 1 and Aim 2, primary inference will be drawn based on intention to treat (ITT) analyses. Average complier effect (ACE) will be used to inform the metformin effect under full compliance to treatment assignments (Angrist et al, 1996). Per protocol analyses will be used to inform the metformin effect among completers. All analyses will be carried out unadjusted and with adjustment for covariates (Table 7) and covariate interactions with treatment and time. Corrections for multiple comparisons will be applied as appropriate.

The impact of metformin treatment on the progression of frailty status (non-frail, pre-frail, frail) over time will be assessed with a repeated measures mixed effects multinomial logistic model that models the log-odds of adjacent frailty statuses in terms of an indicator of metformin use, time, and the metformin use by time interaction. The possibility of non-linear trends of the log-odds of frailty statuses will be assessed by including an additional time factor (e.g., time squared) and its interaction with metformin use. The best fitting model will be used for inference. Secondary outcomes including gait speed, 6 minute walk, SPPB, frailty index constructed from the research data collected according to the Rockwood index (Searle et al., 2008; Rockwood et al., 2007), and body composition will similarly assessed. Under the linear trend model, the beneficial impact of metformin will be revealed by a significant time by treatment interaction associated with the log-odds of frailty status progression, indicating that the rate of increase in the likelihood of frailty progression over time is reduced in the metformin arm relative to the placebo arm. Under the non-linear trend model, the impact of metformin will be revealed by a significant reduction in the log-odds of frailty status progression in the metformin arm versus placebo at certain time points during the follow-up. SAS proc **nlmixed** will be used in the mixed effects model analyses. Proc **nlmixed** is preferred over other mixed effects modeling procedures such as GEE because it is valid under missing at random (MAR) assumption, accommodates linear and non-linear modelling, and uses maximum likelihood estimation.

Table 7. Covariates included in statistical analyses

Categories of covariates	Baseline	Time Varying
Demographics (age, sex)	X	
BMI (obesity), sarcopenia	X	X

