**3.D.6. Time to major adverse event.** The relation between treatment and time to major adverse outcome will be studied with and without adjustment for covariates and will be described with Kaplan-Meier curves. An adverse outcome will be defined as a) 2 point increase in the frailty score, or b) fall resulting in bone fracture or other serious injury, c) admission to a nursing home or skilled care facility, or d) death. The time to adverse outcome will be defined as the time to first occurrence of any of a), b), c) or d) and will otherwise be considered censored at loss to follow-up or end of study. Without adjustment, treatment groups will be contrasted on time to major adverse outcome with a logrank test and the treatment-specific accumulated incidence of adverse outcome will be described with Kaplan-Meier curves and 95% confidence bands. An adjusted contrast of treatment groups will be carried out with a Cox proportional hazards model in terms of treatment group, age, ethnicity, gender, and baseline values of frailty score. OGTT and inflammatory biomarkers will be entered as time-dependent covariates. Logrank testing, Kaplan-Meier estimates of survival distributions, and covariate adjusted Cox modelling of relative risks accommodate non-informative right censored survival data.

**3.D.7. Missing Data.** Limited missingness in outcomes and associated covariates is possible due to loss to follow-up. Missing covariates without loss to follow-up may occur due to missed appointments and intercurrent illness. In the primary analyses, model estimates will be derived based on the likelihood of observed data, an approach that gives consistent estimates under the MAR assumption: “missingness” depending upon the observed data but not the unobserved. To further address the possibility of missing data under the MAR assumption, we will conduct all analyses without and with multiple imputation using SAS proc mianalyze and its companion procedure proc mi. The mianalyze procedure combines the results of the analyses of imputations and generates valid statistical inferences and MI creates multiply imputed data sets for incomplete multivariate data.

**3.D.8. Randomization.** Participants will be randomized to metformin or placebo in a balanced design.

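### Participants who cannot tolerate metformin leave the trial after randomisation, which adds treatment-related missing outcomes that the primary ITT analysis under MAR neither foresees nor tests

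*Combined protocol and SAP*

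**What the plan says.** **The exit rule.** Under the potential risks, item 7 (Administration of metformin): "Subjects who do not tolerate metformin will be disenrolled". The same item provides for titration to the highest dose a person can tolerate.

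**Its timing.** Study Procedures, item i: "After the baseline studies, subjects will be randomized to metformin" or placebo, with titration afterwards. No run-in is described.

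**The one exception.** Study Procedures, item k, deals with confirmed diabetes converters whose HbA1c remains at or above 8 on maximal doses, "or if the patient cannot tolerate metformin and/or pioglitazone". They are referred to their primary care physicians "but will remain in the study for frailty assessment and all other follow-up studies".

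**The analysis.** The Statistical Methods overview states that "primary inference will be drawn based on intention to treat (ITT) analyses". It also plans a complier effect and, for treatment changes, principal stratification and marginal structural models. Section 3.D.7 expects that "Limited missingness in outcomes and associated covariates is possible due to loss to follow-up" and describes the observed-data likelihood as "an approach that gives consistent estimates under the MAR assumption". Multiple imputation is added under the same assumption. Section 3.D.6 relies on methods that "accommodate non-informative right censored survival data".

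**The concern.** An ITT comparison needs outcomes on everyone randomised, or a defensible account of those that are missing. The rule stops frailty measurement because of how a person responded to study drug. That reason may be commoner on metformin, it is not a cause of missing data named in 3.D.7, and intolerance is not among the Table 7 covariates.

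A link between exit and outcome is plausible, though this is inference. Item 7 lists diarrhea, nausea and vomiting as reactions in more than 10%, and after baseline a loss of 5% or more of baseline weight counts as a frailty criterion. Time-varying BMI in the model may absorb part of this. It cannot do so for anyone who leaves before the first post-baseline frailty assessment, which is month 3 in the visit table and month 6 in the text of the frailty section.

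Two things are at stake: possible bias in the arm comparison, and the loss of the data that would show whether there is any. The complier, principal stratification and marginal structural analyses would use the same outcomes, and the time-to-adverse-outcome analysis would treat these exits as uninformative censoring.

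**Working it through.** **1. The plan's own attrition figure.** Aim 1 gives 4-5% drop-out, 600 enrolled and 120 completers. These do not agree:
- 120/(1 − 0.04) = 125.0 and 120/(1 − 0.05) = 126.3 enrolled.
- 600 × 0.96 = 576 and 600 × 0.95 = 570 completers.

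The projected 56-70 people worsening is 47-58% of 120, and section 3.D.3 uses 60 completers per arm, so I work from 120. Leavers are then 125.0 − 120 = 5.0 to 126.3 − 120 = 6.3. If every one were on metformin, that is 5.0/62.5 = 8% to 6.3/63.2 = 10% of the arm. Starting from 600 the count is 24-30, but the ceiling is the same (24/300 = 8%, 30/300 = 10%).

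**2. Crude distortion with no drug effect.** Let p be the worsening risk in both arms, w the risk among leavers, and q the share of the metformin arm lost before any post-baseline visit. The observed metformin rate is (p − qw)/(1 − q), so the distortion is q(p − w)/(1 − q). Take p = (0.47 + 0.58)/2 = 0.525. The values of w and q are assumptions.
- w = 0.85, q = 0.05: 0.05 × (−0.325)/0.95 = −1.7 points (false benefit).
- w = 0.85, q = 0.10: 0.10 × (−0.325)/0.90 = −3.6 points.
- w = 0.20: the same sizes as false harm.
- w = 0.525: zero.
- w = 0.58 or 0.47 (the plan's own limits), q = 0.10: 0.10 × 0.055/0.90 = 0.6 points either way.
- w = 0.85 with placebo losing half as many: −0.9 points at q = 0.05 and −1.9 at q = 0.10.

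**3. False-positive rate with no drug effect.** Simulated trials had 60 per arm, baseline plus five assessments (months 3, 6, 12, 18 and 24 in the visit table, treated as equally spaced), the 3.D.3 placebo steps of 56/22/22 in both arms, and 10% fixed at baseline. A share q in each arm had a different chance of moving up (75% or 33%, assumed). On metformin these people left after 0, 1 or 2 visits. The test was generalised least squares on the 0-5 score with robust standard errors, a stand-in for PROC NLMIXED. One-sided rates against a nominal 2.5%:

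| Loss on metformin | Favouring metformin (up-step 75%) | Favouring placebo (up-step 33%) |
|---|---|---|
| 5% | 2.9-3.7% | 3.0-4.6% |
| 10% | 4.0-5.3% | 4.1-5.4% |

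If the same people are followed to month 24, these rates are 2.1-2.3%. If leavers move like everyone else, they stay at 2.0-2.8%. Section 3.D.3 specifies two-sided 5% testing. On that scale a separate run gave 5.3-5.9% at 5% loss and 5.7-6.6% at 10% loss (up-step 75%).

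**4. If metformin works.** Trials were simulated with the 3.D.3 steps for both arms (60 per arm, five transitions, 130-150 trials per case). They were analysed with a random-intercept adjacent-category logit, reading the treatment-by-time odds ratio. Intolerant participants were assumed to follow the placebo steps and, if disenrolled, to leave after the first post-baseline visit.

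| Intolerant on metformin | Followed | Disenrolled, MAR |
|---|---|---|
| none | 0.18 | not applicable |
| 10% | 0.24 | 0.19 |
| 20% | 0.27 | 0.19 |

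After disenrolment the estimate sits close to the value for a trial in which everyone stays on drug. This set-up did not reproduce the plan's pairing of 86% power with an odds ratio of 0.20: an odds ratio of 0.18-0.20 came with 95-98% power. The comparison within each row is therefore informative, but the absolute values are not.

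**The case against.** The strongest reply is that the word used for exit appears once, undefined, in a risk paragraph. Other text fits continued observation: item k retains intolerant converters, and the complier and marginal structural analyses presuppose data after treatment changes. Consent pages are not in the review copy, so withdrawal wording there cannot be checked. This may be loose drafting. That stands as an explanation, but the rule as written conflicts with item k for intolerant converters and undercuts the declared ITT analysis, so the text still needs reconciling.

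It is also fair that titration to a tolerable dose may confine the rule to a few people, that blinding means some placebo participants may leave too, that this is a pilot, and that likelihood methods are valid if exit is explained by recorded data. These limit the size of the problem. They do not make it checkable.

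Stronger readings that a reader might draw are not supported:
- *The rule is what makes the analysis depend on MAR.* It is not; the overview and 3.D.7 adopt MAR regardless.
- *ITT becomes impossible, or MAR is shown to be false.* Neither follows. Data up to exit can be analysed by assigned arm, and MAR is untested rather than refuted.
- *More than 10% will leave.* That figure is for common adverse reactions, not for disenrolment.
- *Error rates are badly inflated.* Two-sided rates of 6.0-9.5% appear only at 15% loss, a stress case above the 8-10% ceiling.
- *There is no bias if leavers fare like others.* That holds under no drug effect; step 4 shows why it fails if the drug works.

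**Conclusion.** The point holds as a conflict between a stated exit rule and a stated primary analysis. It should be fixed, with medium confidence about its practical weight. Neither the size nor the direction of any bias can be determined from the documents, because they give no intolerance rate by arm.

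Within the only attrition figure available, the effect of the rule on overall type I error is small at 5% loss and modest at 10%, and it rests on assumed prognosis among leavers. With no drug effect, bias needs leavers whose frailty course differs in ways the recorded data do not explain, and it can favour either arm. If metformin works and leavers revert toward the placebo course, the reported effect would be closer to an on-treatment effect than to the ITT effect the plan declares. Outcomes not collected cannot be recovered later, and that is the main reason to act.

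**What to change.** Reconcile item 7 of the risks, item k of the study procedures and the ITT statement by distinguishing stopping study drug from leaving the study. No treatment decision changes.

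- Continue the already scheduled frailty, functional and adverse-outcome assessments to month 24 for all randomised participants unless consent is withdrawn. No clamp or biopsy is required. Analyse these data by assigned arm.
- Report drug stopping and study exit by arm, and by timing relative to the first post-baseline frailty assessment.
- Name disenrolment as a source of missing data in 3.D.7, and add one MNAR sensitivity analysis, for example delta-adjusted imputation by arm, for those who still leave.

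The cost is a wording change, one analysis and up to five scheduled assessments per leaver. At 5-10% of about 63 metformin participants that is roughly 3-6 people and 15-30 visits (3 × 5 to 6 × 5), plus any placebo leavers. The ITT effect will be somewhat diluted. The planned complier analysis can address that more reliably with these outcomes than without them.
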